Specific Aim 2: Demonstrate safety and feasibility of high-intensity interval training (HIIT) in individuals with deployment-related respiratory disease. The same participants described in Aim 1 will complete up to 12 weeks of HIIT. HIIT will include 3 weekly supervised sessions (10 minutes warm-up followed by 4 x 4-minute intervals [4 minutes at 90-95% peak heart rate followed by 3 minutes at 60-75% peak heart rate] followed by 3 minutes cool-down).(7) Participants will also complete three home sessions/week of 40 minutes aerobic exercise at moderate intensity (Borg rate of perceived exertion 12-14. Hypothesis 2A: HIIT is safe and feasible among military personnel suffering from deployment-related respiratory disease, with $\geq 80\%$ participation in prescribed sessions.(8) Hypothesis 2B: Participants will spend approximately 4.5 hours/week engaged in this program and will report that participation was feasible. Hypothesis 2C: Staff will spend approximately 2 hours/participant in exercise supervision and coordination (calculated by [hours spent supervising exercise / number of individuals supervised simultaneously + hours spent scheduling and/or coordinating]. Staff will report that level of supervision and time commitment was appropriate and feasible.

Specific Aim 3: Generate pilot data regarding impact of HIIT on cardiopulmonary performance and its efficacy in improving functional capacity and symptoms in deployment-related respiratory disease. Questionnaire (SF-36), CPET, and peripheral venous metabolomics will be repeated after HIIT intervention. Resting and stress TTE may be performed. Hypothesis 3A: HIIT induces positive right ventricular and pulmonary vascular remodeling, improving right ventricular performance and exertional cardiac output, reflected by decreased glycolytic

metabolites on peripheral venous metabolomics; improved exertional pulmonary artery systolic pressure on TTE (if obtained); and improved oxygen pulse, ventilatory efficiency, and dead space fraction on CPET. Additionally, markers of left ventricular diastolic function on TTE (if obtained) will improve reflecting general positive training adaptations of HIIT.⁽⁸⁾ Hypothesis 3B: HIIT improves VO₂max among patients with deployment-related respiratory disease. Hypothesis 3C: HIIT improves dyspnea and health-related quality of life (SF-36).

II. Background and Significance:

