- Adverse events (recorded at supervised exercise sessions or reported from home sessions)
- Time commitment per participant (for participants, calculated as sum of hours exercising; for staff, calculated as [hours spent supervising exercise / number of individuals supervised simultaneously + hours spent scheduling and/or coordinating for that participant])
- Qualitative feasibility collected via narrative survey of participants and staff

B. Description of Population to be Enrolled:

Men and women ages 18-65 with deployment-related respiratory disease and symptoms of exertional dyspnea or exercise intolerance residing in the Veterans Integrated Service Network (VISN) 19 and receiving some or all of their care at VA medical facilities throughout the Eastern Colorado Health Care System (ECHCS) will be recruited. We will enroll up to 12 eligible veterans.

- **Inclusion Criteria:**

- Deployment of ≥ 30 days to Iraq, Afghanistan, Kuwait, Saudi Arabia, Bahrain, Qatar, United Arab Emirates, Kyrgyzstan, or Djibouti after September 2001(11)
- New onset of cough, shortness of breath, chest tightness/wheezing, dyspnea on exertion or exercise intolerance which started during or after deployment(11)
- Definite or probable distal lung disease (≥ 1 hyperinflation, emphysema, bronchiolitis, small airways inflammation, peribronchiolar fibrosis, or granulomatous pneumonitis on surgical lung biopsy; or ≥ 2 centrilobular nodularity, air trapping, mosaicism, or bronchial wall thickening on chest CT),(11) definite or probable deployment-related asthma (≥ 1 increase in post-bronchodilator forced expiratory volume in 1 second [FEV₁] $\geq 12\%$ and ≥ 200 cc, or methacholine challenge with PC₂₀ FEV₁ ≤ 16 mg/mL)(11) or unexplained dyspnea on exertion or exercise intolerance despite noninvasive testing including pulmonary function testing, methacholine challenge, transthoracic echocardiography, and/or chest computed tomography(9, 13)
- Current symptoms of dyspnea on exertion or exercise intolerance
- Residence <90 miles from RMR VA and ability / willingness to attend in-person HIIT sessions and research visits

- **Exclusion criteria:**

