Anticipated risks of HIIT training include fatigue, shortness of breath and leg discomfort, and participants will be counseled of these risks. Additionally, study team will closely monitor for adverse events through observation as well as participant report. Adverse events will include the following: minor – hypotension (BP < 90/60), lightheadedness, hypoxemia (SpO₂ <80% for >60 seconds),(24) chest pain, arrhythmia, or need to terminate exercise for another reason; major – major adverse cardiac event (stroke, myocardial infarction or cardiovascular death) or hospitalization. Exercise session will be terminated for any minor adverse event and PI and study safety monitor will be notified. Patient will be referred to Emergency Room if any member of the study team or the participant feel referral is indicated. Additionally, participant will be evaluated by PI prior to engaging in any future sessions. If further participation is felt to be of risk to the patient by either PI or the study’s safety monitor, then participation in study will be terminated. Major adverse events are not anticipated, but if any should occur patient will be transported immediately to the Emergency Room. HIIT has been studied in various populations including those with good health but sedentary lifestyle,(8) moderate to severe asthma,(17) and coronary artery disease,(25) and similar or identical HIIT regimens to that described in this protocol studies have demonstrated >80% compliance without attributable adverse events.(8, 25) Additionally, the study design includes an initial baseline assessment with symptom-limited CPET. If the initial CPET identifies safety concerns with completing the study exercise protocol, those concerns will be addressed prior to participant completing any further intervention. If unable to be addressed then the participant will be removed from the study. Therefore, the proposed protocol is anticipated to be safe for participants.

Home exercise: In addition to HIIT sessions described above, participants will perform three sessions / week of 40 minutes aerobic exercise at moderate intensity (Borg rate of perceived exertion 12-14). Home exercise will be prescribed to minimize the risk of confounding from

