Hypothesis 1B: Increased right ventricular afterload causes maladaptive right ventricular remodeling which is reflected by increased glycolytic metabolites (compared to a reference healthy population).(2, 3) Metabolomics partial least squares discriminant analysis and t-test or ANOVA will be performed. Exercise metabolomics data collected in a healthy population (COMIRB 21-4354) will be used as a reference.

Hypothesis 1C: Impaired right ventricular performance contributes to reduced maximum oxygen consumption (VO2max) relative to healthy population norms, dyspnea and impaired health-related quality of life. VO2max will be analyzed using descriptive statistics and presented in reference to healthy population norms (ATS/ACCP guidelines).(6) Dyspnea and health-related quality of life will be assessed by SF-36 with scores analyzed by descriptive statistics. Scores will be presented in

reference to disease population references.(34, 35) Linear mixed models will be used to assess the relationship between impaired right ventricular performance as measured by pulmonary artery systolic pressure and VO2max. Covariates including BMI, gender, age and type of deployment-related respiratory disease will be included.

Specific Aim 2:

Hypothesis 2A: *HIIT is safe and feasible among military personnel suffering from deployment-related respiratory disease, with $\geq 80\%$ participation in prescribed sessions.*(8) Attendance will be calculated as (number of supervised sessions attended + unsupervised sessions reported by exercise diary) / total number of supervised + unsupervised sessions. Feasibility will be based upon attendance of $>80\%$ of prescribed exercise sessions, with separate analyses for HIIT sessions, “light exercise” sessions, and combined sessions. Safety/acceptability will be based upon an absence of major adverse events attributable to the exercise training program and $<5\%$ minor adverse events (calculated as the number of adverse events divided by the total number of exercise sessions throughout the program) attributable to the exercise training program.

Hypothesis 2B: *Participants will spend approximately 4.5 hours/week engaged in this program and will report that participation was feasible.* Total hours spent in exercise program will be calculated based upon number of supervised sessions and reported unsupervised sessions. Qualitative assessment of feasibility will be collected via narrative report.

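### The <5% minor-event criterion behind the statement that HIIT is safe pools HIIT with an equal number of moderate home sessions, so it describes the combined program and not HIIT

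*Combined protocol and SAP*

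**What the plan says.** Specific Aim 2 (section I) is to "Demonstrate safety and feasibility of high-intensity interval training (HIIT) in individuals with deployment-related respiratory disease". The Data Analysis Plan (section III) repeats Hypothesis 2A, that HIIT is safe and feasible, and sets two safety conditions:

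- **Major events.** "Safety/acceptability will be based upon an absence of major adverse events attributable to the exercise training program". This condition has no denominator.
- **Minor events.** Attributable minor events must be below 5%, "calculated as the number of adverse events divided by the total number of exercise sessions throughout the program".

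The program has two components of equal frequency. Under Aim 2, "HIIT will include 3 weekly supervised sessions"; under Home exercise (section III.D), "participants will perform three sessions / week of 40 minutes aerobic exercise at moderate intensity". Both run for up to 12 weeks. The Outcome Measures list covers events from both: "Adverse events (recorded at supervised exercise sessions or reported from home sessions").

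The sentence just before the safety criteria sets the attendance threshold as a share "of prescribed exercise sessions, with separate analyses for HIIT sessions", light sessions and combined sessions. No such split is given for minor events, and no other section plans a minor-event rate for HIIT sessions alone.

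**The concern.** The hypothesis is about HIIT, but about half of the denominator of its minor-event rate is not HIIT. HIIT intervals run at 90-95% of peak heart rate, while home sessions are moderate (Borg 12-14). It is therefore plausible, though the documents do not show it, that minor events will concentrate in the HIIT sessions. Home sessions would then enlarge the denominator and add little to the numerator.

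What is at stake is the wording of the result. Section III.F says the study will demonstrate the safety of HIIT in this population and help to justify a randomized trial comparing exercise modalities. A reader planning that trial would want the event rate per HIIT session. As planned, both safety conditions could be met and HIIT called safe while the rate in HIIT sessions was well above 5 per 100, with no planned analysis to show it.

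**Working it through.** The plan states no session total, event limit or operating characteristic for this rule, so there is no figure to reproduce. The inputs are the plan's own schedule: 12 participants, 12 weeks, 3 HIIT and 3 home sessions per week. As a cross-check, section III.D (Subject compensation) gives up to 27 hours of supervised and 27 hours of home exercise. These sum to 54 hours, and 54/12 = 4.5 hours per week, which agrees with Hypothesis 2B and with an equal split.

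**Sessions.** HIIT: 12 × 12 × 3 = 432. Home: 12 × 12 × 3 = 432. Total: 864.

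**Events allowed by the pooled rule.** 43/864 = 4.98% passes and 44/864 = 5.09% fails, so the limit is 43.

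**HIIT-session rate at 43 events.**
- All in HIIT: 43/432 = 9.95 per 100. This is the ceiling.
- About a quarter at home (11 home, 32 HIIT): 32/432 = 7.41 per 100.
- Equal rates in both types: no dilution.

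With equal session numbers the pooled rate is (h + m)/2, where h is the HIIT rate and m the home rate. The rule therefore passes whenever h + m is below 10 per 100.

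**If sessions performed are the denominator.** The plan does not say whether prescribed or performed sessions are counted. The attendance levels below are assumptions.

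| HIIT / home attendance | Sessions | Maximum events | HIIT rate if all events in HIIT |
|---|---|---|---|
| 80% / 80% | 346 + 346 = 692 | 34 (4.91%) | 34/346 = 9.8 per 100 |
| 100% / 80% | 432 + 346 = 778 | 38 (4.88%) | 38/432 = 8.8 per 100 |
| 80% / 100% | 346 + 432 = 778 | 38 (4.88%) | 38/346 = 11.0 per 100 |

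**How often the pooled rule would mask a high HIIT rate.** At full attendance the observed HIIT rate exceeds 5% from 22 HIIT events (22/432 = 5.09%; 21/432 = 4.86%). The probability that the pooled rule passes while the observed HIIT rate exceeds 5% is the sum over x = 22 to 43 of P(HIIT events = x) × P(home events ≤ 43 − x). Counts are independent Poisson with means 4.32 × rate per 100. The true rates are assumed.

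| True HIIT rate per 100 | Home 0 | Home 1 | Home 2 |
|---|---|---|---|
| 6 | 0.80 | 0.79 | 0.74 |
| 7 | 0.94 | 0.88 | 0.72 |
| 9 | 0.77 | 0.53 | 0.28 |
| 11 | 0.29 | 0.12 | 0.04 |

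The probability falls at higher rates because the pooled rule itself then begins to fail.

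**Where pooling does no harm.** At true HIIT rates of 2-3 per 100 with 0-2 per 100 at home, the observed pooled rate and the observed HIIT rate each fall below 5% with probability 0.986 or more. With 5 per 100 in both session types, the chances of falling below 5% are nearly the same: 0.53 pooled and 0.51 for HIIT alone.

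**The case against.** The strongest reply is that the criterion is coherent as a program criterion. Both safety conditions refer to events attributable to the exercise training program. The home sessions are prescribed under the HIIT exercise intervention heading in section III.C, and the 4.5 hours per week of Hypothesis 2B counts them. Home events also enter the numerator. On this reading, HIIT is shorthand for the delivered regimen. That stands as a defence of the pooled rate. It does not supply a rate for HIIT sessions, and the plan thought the distinction worth making for attendance.

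The second reply is that few events are expected. On similar or identical regimens, section III.D says "studies have demonstrated >80% compliance without attributable adverse events". The observed HIIT rate can exceed 5% under a pooled pass only with 22 to 43 HIIT events, or 1.8 to 3.6 per participant (22/12 and 43/12). Each minor event ends the session, is notified to the investigator and safety monitor, and leads to evaluation before further sessions. The safety monitor also reviews the study after six participants. So many events would not go unnoticed, and the constant-rate Poisson model ignores this feedback. This limits how likely the problem is, but the Hypothesis 2A result could still read as a pass.

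A reader might infer three stronger things that the documents do not support:

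- **That a HIIT rate above 5 per 100 breaches the plan's limit.** The plan defines 5% only over all sessions and has no HIIT-only limit.
- **That pooling already misleads at true HIIT rates of 3-4 per 100.** An observed HIIT rate above 5% would then be sampling noise, and a pooled pass would be the right answer.
- **That participants are less protected.** The event-by-event procedures and the safety monitor's reviews do not use this ratio.

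**Conclusion.** The concern holds in a limited form. The minor-event rate is a valid summary of the combined program, but it cannot support a statement specific to HIIT. At full attendance it passes with a HIIT-session rate of up to 9.95 per 100, or 8.8 to 11.0 if one or both session types are attended at 80%. These ceilings follow from the schedule and assume that no event occurs at home.

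Whether it matters in practice depends on rates the documents do not give. It needs a true HIIT rate above 5 per 100 and a lower home rate. With 0-2 per 100 assumed at home, the pooled rule passes while the observed HIIT rate exceeds 5% with probability 0.74-0.80 at a true HIIT rate of 6 per 100, 0.72-0.94 at 7 and 0.28-0.77 at 9. At the low rates the plan expects, the effect is negligible. The major-event condition is unaffected. This is worth correcting because the conclusion and the measure do not match and the correction is small.

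**What to change.** In the Data Analysis Plan under Hypothesis 2A:

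1. Report attributable minor-event rates separately for HIIT sessions, home/light sessions and all sessions combined, as already planned for attendance.
2. Classify each session by the type performed, so that light sessions substituted for HIIT after injury (Potential Scientific Problems, Feasibility of exercise training program) count as light. Some events may surface only when participants are questioned at the 4-week diary collection. Show those that cannot be linked to a session type separately, and count them in the combined rate.
3. State whether denominators are prescribed or performed sessions.
4. Keep the <5% criterion on the combined rate and word that conclusion as safety of the combined exercise program. Base any HIIT-specific safety statement on the HIIT-session rate, alongside the unchanged major-event condition.

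The cost is analysis-plan wording, an allocation rule for events and a little extra tabulation; events are already collected from both supervised and home sessions. The HIIT rate will be less precise, resting on 432 sessions at most instead of 864, and the HIIT statement may be less favourable. Holding the HIIT rate itself to <5% (at most 21 of 432) is optional: it would be a new, stricter limit for which the documents give no basis.

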The proposed study is a single-arm clinical trial to generate pilot data regarding the safety, feasibility and efficacy of an exercise intervention. Participants will complete a baseline assessment (Visits 1A +/- 1B) at 0 weeks followed by up to 12 weeks of HIIT intervention followed by a repeat assessment (Visits 2A +/- 2B). An overview of the study protocol is provided in Figure 1.

Figure 1: Protocol Overview

Visits 1A/1B and 2A/2B: Visits 1A and 2A will be performed in the inpatient unit of the Clinical and Translational Research Center at the University of Colorado. Each visit will include administration of SF-36 questionnaire, spirometry, and a cardiopulmonary exercise test. Peripheral IV will be placed for the purpose of venous blood draws for complete blood count, ferritin and untargeted metabolomics analysis.(1) Radial arterial line will be placed for continuous blood pressure monitoring and measurement of arterial blood gas and lactate. Participants will be oriented to VO2max testing protocol. Baseline fitness will be assessed by questioning to determine step protocol. Once arterial line is in place, participants will complete a symptom-limited CPET on an upright stationary bicycle. Workload will begin at 0 Watts and increase every minute by 10-30 W (based upon pre-testing questioning) to achieve volitional exhaustion with maximum workload at 8-12 minutes.(22) Heart rate and rhythm, blood pressure, oxygen saturation, and gas exchange parameters (VO2, VCO2, and minute ventilation) will be continuously measured. Borg RPE, arterial blood gas and lactic acid will be measured at rest, every 4 minutes during exercise, and at peak exertion. Attainment of a high-quality VO2max will be determined based upon achieving one or more of the following: a plateau in VO2; attainment of predicted VO2max, work rate, or heart rate; respiratory exchange ratio >1.15, and Borg Scale rating 9-10 on a 0-10 scale.(6) Peripheral venous blood draw for untargeted metabolomics analysis will be repeated at peak exercise.

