Peripheral venous blood sample collection: Peripheral venous blood samples will be collected during Visits 1A and 2A. Samples will be collected from the peripheral IV. Five samples of 3-5 cc each will be collected at rest and two samples of 3-5 cc each will be collected after maximal exercise (a total of 7 samples = 21-35 cc blood). One sample from rest will be used to obtain a complete blood count and ferritin. One sample from each timepoint will be saved for storage in a -80° C freezer accessible to the study investigators in University of Colorado Research Complex Building 2 for future analyses. The other two samples will be processed via 2000 g centrifuge for 10

minutes at 4° C. Plasma and red blood cells will be isolated into separate tubes prior to storage in the same -80° C freezer. The plasma and RBC samples will be transported later to the University of Colorado School of Medicine Metabolomics Core lab. Metabolomic assessment will be performed using Vanquish ultra-high-performance liquid chromatography coupled to Q Exactive mass spectrometry (UHPLC-MS; Thermo Fisher Scientific, San Jose, CA, United States). Additionally, two samples will be used for isolation of monocytes/macrophages (one will be placed in an EDTA tube for separation into red blood cells, monocytes/macrophages, and plasma and one in an untreated tube for plasma; both will be separated via a Ficoll gradient technique and resuspended in RPMI media). Risks of peripheral venous blood sample collection include pain and bleeding.

Echocardiography: Transthoracic echocardiography may be utilized in Visits 1B and 2B to collect information on right and left ventricular function at rest and immediately after peak exercise. It is possible that participants may feel slight discomfort from a probe sitting over the skin.

COVID-19 rapid antigen testing: According to outpatient CTRC facility guidelines, immediately prior to Visits 1B and 2B participants may be asked to perform a COVID-19 rapid antigen test. If positive, the visit will be terminated and rescheduled. Participants will self-administer COVID-19 test by gently inserting a cotton swab into both nares. Risks include discomfort or inconvenience at identifying asymptomatic COVID-19 infection.

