Hypothesis 2C: *Staff will spend approximately 2 hours/participant in exercise supervision and coordination. Staff will report that level of supervision and time commitment was appropriate and feasible.* Staff time spent in exercise supervision will be calculated by [hours spent supervising exercise / number of individuals supervised simultaneously + hours spent scheduling and/or coordinating]. Staff's qualitative assessment of feasibility will be collected via narrative report.

Specific Aim 3:

Hypothesis 3A: *HIIT induces positive right ventricular and pulmonary vascular remodeling, improving right ventricular performance and exertional cardiac output, reflected by decreased glycolytic metabolites on peripheral venous metabolomics; improved exertional pulmonary artery systolic pressure on TTE; and improved oxygen pulse, ventilatory efficiency, and dead space fraction on CPET. Additionally, markers of left ventricular diastolic function on TTE will improve reflecting general positive training adaptations of HIIT.*(8) Metabolomics heat maps, partial least squares discriminant analysis, and t-test or ANOVA will be performed to compare pre- vs post-exercise training glycolytic metabolites. Pulmonary artery systolic pressure on TTE and oxygen pulse, ventilatory efficiency, and dead space fraction on CPET will be analyzed using descriptive statistics and compared pre- and post-exercise program by t-test. Resting left ventricular diastolic function (E/e') will be analyzed using descriptive statistics and compared pre- and post-exercise training by t-test.

Hypothesis 3B: *HIIT improves VO2max among patients with deployment-related respiratory disease.* VO2max will be analyzed using descriptive statistics and compared pre- and post-exercise training by t-test.

Hypothesis 3C: *HIIT improves dyspnea and health-related quality of life (SF-36).* SF-36 pre- and post-exercise training will be analyzed using descriptive statistics and compared pre- and post-exercise training by t-test.

Results will be analyzed according to an intention-to-treat protocol. A p-value of <0.05 will be used to establish statistical significance. Statistical analysis will be performed using SAS v 9.4 (SAS Institute Inc., Cary, NC, USA). For metabolomics data, the MetaboAnalyst 4.0 package will be used for analysis and XY graphs will be created using GraphPad Prism 8 (GraphPad Software Inc., La Jolla, CA, United States).

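### Hypothesis 3A metabolomics compares the same participants before and after training but names the independent-groups methods of 1B, so the pairing of samples is ignored

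*Combined protocol and SAP*

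**What the plan says.** Section III.C describes one group measured twice: "The proposed study is a single-arm clinical trial to generate pilot data regarding the safety, feasibility and efficacy of an exercise intervention". Blood for metabolomics is drawn at rest and again at peak exercise, at Visit 1A and at Visit 2A. Each completer therefore has up to four metabolomic sampling points.

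The Data Analysis Plan treats metabolomics in two places.

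- Hypothesis 1B: "Metabolomics partial least squares discriminant analysis and t-test or ANOVA will be performed". The comparator is other people: "Exercise metabolomics data collected in a healthy population (COMIRB 21-4354) will be used as a reference".
- Hypothesis 3A: "Metabolomics heat maps, partial least squares discriminant analysis, and t-test or ANOVA will be performed to compare pre- vs post-exercise training glycolytic metabolites". The comparator is the same people at the earlier visit.

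The remaining pre-post outcomes in Aim 3 are tested by a t-test of unstated type. Pulmonary artery pressure and the exercise gas-exchange measures "will be analyzed using descriptive statistics and compared pre- and post-exercise program by t-test", and E/e' is handled in the same way. For the primary outcomes the plan says "VO2max will be analyzed using descriptive statistics and compared pre- and post-exercise training by t-test" and "SF-36 pre- and post-exercise training will be analyzed using descriptive statistics and compared pre- and post-exercise training by t-test". None of these is described as paired, repeated-measures or within-person. Linear mixed models appear only in Hypothesis 1C.

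**The concern.** 1B and 3A ask different statistical questions. In 1B the two sets of samples come from different people, so independent-groups methods fit. In 3A every post-training sample has a pre-training partner from the same person, and the quantity of interest is the within-person change. Ordinary PLS-DA receives a visit label for each sample and no participant label, so stable differences between people count as noise around the training effect. An ordinary ANOVA or two-sample t-test does the same with its error variance.

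The rest and peak samples add a second layer. The plan does not say whether the two sampling times are analysed separately, jointly or pooled. At stake is whether the 3A metabolite results, which are meant to support the remodelling hypothesis and inform a larger study, have a valid error term and use the information that 12 self-paired participants provide.

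**Working it through.** **1. The plan's own figure.** The Sample Size paragraph gives N = 10 for 90% power to detect a VO2max change of 2 ml/kg/min with SD 1.8, alpha 0.05 and up to 10% dropout. It does not say whether 1.8 is the SD of change, and I take the test as two-sided.

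- Paired, normal approximation: n = [(1.960 + 1.282) × 1.8 / 2]² = 8.5, so 9. Then 9 / 0.90 = 10. This matches.
- Independent groups: n = 2 × 8.51 = 17.0, so 18 per time point (19 with the exact t-test). This does not match.

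The VO2max sample size therefore rests on a within-person comparison, although the analysis text does not name one.

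**2. Metabolomics inputs.** The documents give no effect size, SD or pre-post correlation for any metabolite. Steps 3 and 4 use assumed values and show a range.

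**3. One sample per visit.** Let σ be the SD at one visit, ρ the pre-post correlation and n = 12. The true variance of the mean change is 2σ²(1 − ρ)/n. An unpaired test uses 2σ²/n, which is too large by a factor of 1/(1 − ρ) when ρ is positive. For an assumed true change of 0.8σ, the paired noncentrality is 0.8√12 / √[2(1 − ρ)]. Paired power below comes from the noncentral t distribution, and the unpaired columns from simulation (200,000 runs per cell, two-sided 0.05).

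| ρ (assumed) | Noncentrality, paired | Power, paired | Power, unpaired | True type I error, unpaired |
|---|---|---|---|---|
| 0.3 | 2.34 | 57% | 46% | 2.2% |
| 0.5 | 2.77 | 71% | 46% | 0.9% |
| 0.7 | 3.58 | 90% | 45% | 0.2% |

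The unpaired test loses about one fifth, one third and one half of the paired power respectively. At ρ = 0 it loses nothing (47% unpaired, 43% paired).

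**4. Rest and peak samples pooled.** Twelve people, two visits and two sampling times give 12 × 2 × 2 = 48 samples, or 24 per visit. Split a total variance of 1 into person (P), person-by-visit (V) and residual (E) parts, with no rest-to-peak shift in the mean. The true variance of the visit difference is (2V + E)/12. A test that treats all 24 samples per visit as independent uses (P + V + E)/12 = 0.083. The test is thus anti-conservative when V exceeds P and conservative when P exceeds V. Simulated type I error (100,000 runs) at nominal 5%:

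| P / V / E (assumed) | True variance | Type I error |
|---|---|---|
| 0.5 / 0.2 / 0.3 | 0.058 | 3% |
| 0.2 / 0.5 / 0.3 | 0.108 | 9% |
| 0.1 / 0.7 / 0.2 | 0.133 | 13% |

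The direction of the error cannot be settled from the documents.

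**The case against.** The strongest reply is that the plan is silent rather than wrong. The terms t-test and ANOVA cover paired and repeated-measures forms, the study has one arm, and step 1 shows that the team sized VO2max on a within-person change. For VO2max, SF-36, the exercise-test measures and echocardiography, this stands. A reader might infer that every pre-post analysis treats repeated measurements as coming from different people. The documents do not say so, and the sample-size calculation points the other way for VO2max. That part is a wording gap.

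The reply is weaker for 3A metabolomics. PLS-DA as named has no pairing in its ordinary form, the method list is the one used for an independent comparator in 1B, and no sample-size or modelling text points to a within-person analysis. The handling of rest and peak samples is also open.

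Two further objections are fair. The t-test figures above do not measure how PLS-DA performs, so they show the mechanism and its likely order of size only. This is also a hypothesis-generating pilot, so no confirmatory claim hangs on the metabolite tests. That lowers the stakes, but a cheap and clear improvement is still available.

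**Conclusion.** The point holds for 3A metabolomics. The plan names methods suited to different people for a comparison within the same people, and in their ordinary form these give the wrong error term. With one sample per visit and positive correlation the consequence is a conservative test. Under the assumed 0.8 SD change in 12 people, power is about 46% where a paired test would have 57% to 90% for correlations of 0.3 to 0.7. With rest and peak samples pooled, the test may be conservative or anti-conservative.

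A reader might go further and conclude that most of the power is lost. The figures show a loss of about a fifth to a half over the range examined, and the inputs are assumptions. A reader might also calculate that an unpaired VO2max test would have about 1% power. That requires an assumed between-person SD of 5 ml/kg/min or more, which the documents do not give, and it concerns the outcome for which pairing is most clearly implied.

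**What to change.** For Hypothesis 3A metabolomics:

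- Test each metabolite with a paired test, separately at rest and at peak. Alternatively, fit a linear mixed model with a participant random effect and fixed effects for visit, sampling time and their interaction.
- Replace ordinary PLS-DA with within-person (multilevel) PLS-DA, and assess it by permuting visit labels within participant.
- State that rest and peak samples are not pooled as independent observations.

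Keep the independent-groups methods for Hypothesis 1B. As a clarification only, write paired t-test for the other Aim 3 pre-post comparisons, and say whether the 1.8 ml/kg/min in the Sample Size paragraph is the SD of change.

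The cost is a few sentences in the Data Analysis Plan and a little more analysis work. No new data, samples or visits are needed. A simple paired test per metabolite would meet the main need if the team prefers to avoid the mixed model.
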